10.2. Adverse Event Reporting

All subjects must be carefully monitored for AEs as defined below. Sufficient information must be obtained by the Investigator to determine whether the event meets criteria for immediate reporting to the sponsor (ie, SAEs and pregnancies). All AEs should be assessed in terms of their seriousness, severity, and relationship to the study drug, per the definitions in the following sections.

10.2.1. Safety Reporting Definitions

10.2.1.1. Adverse Events

An AE is defined as any untoward medical occurrence in a subject administered a medicinal product that does not necessarily have a causal relationship with this treatment. An AE can, therefore, be any unfavorable and unintended sign (including an abnormal laboratory finding), symptom, or disease temporally associated with the use of an investigational product, whether or not related to the investigational medicinal product.

Adverse events may include worsening or exacerbation of the disease under study; worsening or exacerbation of preexisting conditions or events; intercurrent illnesses; or drug interactions. Anticipated fluctuations of preexisting conditions that do not represent a clinically significant exacerbation or worsening are not considered AEs.

Adverse events should be recorded using medical terminology and whenever possible, a diagnosis should be provided for clearly associated signs, symptoms, and/or abnormal laboratory results. If the final diagnosis is not known at the time of initial detection, the provisional diagnosis or signs or symptoms should be recorded and updated when the final diagnosis is available.

Surgical procedures are not AEs; they are therapeutic measures for conditions that require surgery. The condition, provided it develops or is a worsening of a preexisting condition for which the surgery is required, is the AE.

10.2.1.2. Serious Adverse Events

A serious adverse event (SAE) is any untoward medical occurrence that at any dose:

- Is fatal (results in death)
- Is life-threatening: The subject was at immediate risk of death from the AE as it occurred. This does not include an event that, had it occurred in a more severe form, or was allowed to continue, might have caused death.
- Requires inpatient hospitalization or prolongation of existing hospitalization (in the absence of a precipitating, clinical AE hospitalization is not in itself an SAE)

- Results in persistent or significant disability/incapacity
- Is a congenital anomaly/birth defect (in the child of a subject who was exposed to the study treatment)
- An important medical event that may not result in death, be life threatening, or require hospitalization may be considered an SAE when, based upon appropriate medical judgment, the event may jeopardize the subject and may require medical or surgical intervention to prevent one of the outcomes listed in this definition. Examples of such events are intensive treatments in an emergency room or at home for allergic bronchospasm, blood dyscrasias, or convulsions that do not result in hospitalization, or development of drug dependency or drug abuse.

An SAE does not include:

- Progression of disease (See Section 10.2.2.9)
- Hospitalization for a routine clinical procedure
- Pre-planned treatments or surgical procedures requiring hospitalization (the conditions should be documented as appropriate in the eCRF)
- Hospitalization for non-medical reasons (ie, social admissions, hospitalizations for social, convenience or respite care)

10.2.1.3. Special Situation Reports

Special situation reports (SSRs) include all reports of medication error, abuse, misuse, overdose, occupational exposure, drug interactions, exposure via breastfeeding, unexpected benefit, transmission of infectious agents via the product, counterfeit of falsified medicine, and pregnancy regardless of an associated AE.

Medication error is any unintentional error in the prescribing, dispensing, preparation for administration or administration of a study drug while the medication is in the control of a health care professional, patient, or consumer. Medication errors may be classified as a medication error without an AE, which includes situations of missed dose, medication error with an AE, intercepted medication error, or potential medication error.

Abuse is defined as persistent or sporadic intentional excessive use of a study drug by a subject.

Misuse is defined as any intentional and inappropriate use of a study drug that is not in accordance with the protocol instructions or the local prescribing information.

An overdose is defined as an accidental or intentional administration of a quantity of a study drug given per administration or cumulatively that is above the maximum recommended dose as per protocol or in the product labeling (as it applies to the daily dose of the subject in question).

In cases of a discrepancy in drug accountability, overdose will be established only when it is clear that the subject has taken the excess dose(s). Overdose cannot be established when the subject cannot account for the discrepancy, except in cases in which the investigator has reason to suspect that the subject has taken the additional dose(s).

Occupational exposure is defined as exposure to a study drug as a result of one's professional or nonprofessional occupation.

Drug interaction is defined as any drug/drug, drug/food, or drug/device interaction.

Unexpected benefit is defined as an unintended therapeutic effect where the results are judged to be desirable and beneficial.

Transmission of infectious agents is defined as any suspected transmission of an infected agent through a sponsor study drug.

Counterfeit or falsified medicine is defined as any study drug with a false representation of (a) its identity, (b) its source, or (c) its history.

10.2.2. Adverse Event and Special Situation Reporting

10.2.2.1. Requirements for Collection of Events Before Study Drug Initiation

After informed consent, but before initiation of study drug, the following types of events must be reported on the applicable eCRFs: all SAEs and any AEs that are related to protocol-required procedures.

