4.3. Study Procedures

Enrollment occurs upon completion of all screening procedures. Enrollment will be performed centrally by an interactive web response system (IWRS). Clear documentation as to the reason the subject was not dosed should be provided on the relevant eCRF. Unless otherwise specified, collection windows for laboratory assessments prior to dosing may be obtained up to 3 days prior to dosing. Treatment (dosing) may be permitted either 1 day before or within 7 days after scheduled visits.

An infectious disease pandemic may pose additional risks to study drug availability, the study visit schedule, and adherence to protocol-specified safety monitoring or laboratory assessments. Refer to [Appendix 2](#) for further details on the risks and risk mitigation strategy.

For safety parameters, please refer to Section [10.1](#).

Table 1. Schedule of Assessments

Phase	Pre-Treatment	Treatment			Unscheduled Visit	End of Treatment ^a	Safety Follow-up ^b	End of Study ^a
		Treatment Cycle 1 through Last Cycle (21-day cycle)		Day 8				
Period	Screening	Day 1 (includes baseline C1D1)	Day 8					
Day	Days -21 to 1							
Informed consent	X							
Inclusion and exclusion criteria	X							
Prior sacituzumab govitecan parent study	X							
Weight		X						
Hematology ^c		X	X	X	X	X		
Serum chemistry ^d		X	X	X	X	X		
Urine pregnancy test ^e	X	X		X	X	X	X	X
FSH ^f	X							
Sacituzumab govitecan administration		X	X					
Concomitant medications		Throughout Study						
SAEs ^g		Throughout Study						
AEs ^g		Throughout Study						

AE = adverse event; C1D1= Cycle 1 Day 1; FSH = follicle-stimulating hormone; SAE = serious adverse event

a End of treatment (EOT) visit approximately 30 days of the last dose of the study drug. For the definition of End of Study (EOS), refer to Section 3.6.

b For subjects of childbearing potential, the Safety Follow-up visits will be every 28 days for 6 months after study drug discontinuation. For subjects of non-childbearing potential who have ongoing AEs or SAEs at EOT, the Safety Follow-up visits will be every 6 weeks for up to 6 months after study drug discontinuation or until the criteria for EOS (Section 3.6) have been met. Subjects of non-childbearing potential who do not have ongoing AEs or SAEs at EOT will be considered as having reached EOS.

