10.2.2.2. Reporting Period for Adverse Events

Following initiation of study drug, collect all AEs, regardless of cause or relationship, until 30 days after last administration of study drug and report the AEs on the eCRFs as instructed.

All AEs and clinically significant laboratory abnormalities should be followed until resolution or until the AE is stable, if possible. Gilead may request that certain AEs be followed beyond the protocol-defined follow-up period.

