10.2.2.5. Adverse Event Collection and Documentation

Adverse Events Reporting Process

It is the responsibility of the Investigator to document all AEs that occur during the study. All adverse events regardless of seriousness, severity, or relationship to the study drug, that occur during the safety reporting period, must be recorded in the AE page of the eCRF. AEs should be elicited by asking the subject a non-leading question (eg, “have you experienced any new or changed symptoms since we last asked/since your last visit?”). AEs can also represent abnormal findings from laboratory tests and other study procedures. The Investigator must review all laboratory and test data; abnormal findings should be assessed to determine if they meet the criteria for adverse events (Section 10.2.1.1, Section 10.2.2.8).

For all AEs, the Investigator must pursue and obtain information adequate to assess whether it meets the criteria for classification as an SAE and, therefore, requires immediate notification to the sponsor or its designee (Section 10.2.5). In addition, sufficient information must be obtained by the Investigator to perform a causality assessment, which must be done for every adverse event. Follow-up by the Investigator is required until the event or its sequelae resolve or stabilize, as assessed by the Investigator. The outcome of each AE must be provided on the eCRF.

To assist in the sponsor’s assessment of each case, further information may be requested from the Investigator to provide clarity and understanding of the event in the context of the clinical study.

Adverse events and SAEs resulting from SSRs must be reported in accordance with the AE and SAE reporting guidance summarized in Sections 10.2.2.5 and 10.2.5.

Serious Adverse Events Reporting Process

SAEs are to be recorded on the eCRF and SAE form. The SAE form must be forwarded to the sponsor or the sponsor's designee in accordance with the timelines summarized in Section 10.2.5. The Investigator should include a detailed description of the event(s), including the clinical course, criteria for seriousness, treatments administered, action taken with respect to study drug, rationale for the Investigator's assessment, including causality, and other relevant information, such as possible alternative etiologies.

Information captured on both the SAE form and entered into the eCRF should be consistent.

Special Situation Reporting Process

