11.3.3. Safety Analyses

Safety analyses will be based on All Treated Subjects. All safety analyses will be presented by cancer types and histology when deemed appropriate. Safety data will be summarized using descriptive statistics. Categorical variables will be summarized by number and percentage. Continuous variables will be summarized using n (number of subjects with available data), mean, standard deviation, median, upper and lower quartiles, and range (minimum and maximum), unless otherwise specified.

A treatment-emergent AE will be defined as any AE that begins on or after the date of first dose of study drug up to the date of last dose of study drug plus 30 days. Treatment-emergent laboratory abnormalities will be defined as values that increase at least 1 toxicity grade from baseline at any time after baseline up to and including the date of last dose of study drug plus 30 days. Treatment-emergent AEs and SAEs and clinical laboratory test results will be summarized. Study drug exposure and concomitant medications will also be summarized.

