5.2. Previous Immunomedics (Parent) Study Information

A by-subject listing will be provided for all subjects enrolled into the study, including previous study protocol number, previous subject number, previous site number, last cycle received while on parent study, last dose of sacituzumab govitecan in parent study and date of last dose of sacituzumab govitecan in parent study. If available, the date of first dose of sacituzumab govitecan in parent study, number of dose reduction and each dose reduction date and reason in parent study will also be listed.

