6.2. Adverse Events

Treatment-emergent adverse events (TEAEs) are defined as any AEs that begin or worsen on or after the start of study drug through 30 days after the last dose of study drug. All AEs will be coded using Medical Dictionary for Regulatory Activities (MedDRA). The severity will be graded based on the National Cancer Institute's (NCI) Common Terminology Criteria for Adverse Events (CTCAE) v5.0. Only TEAEs will be summarized and will be referred to as AEs hereafter.

The frequency and severity of AEs, classified by MedDRA, will be summarized using MedDRA Preferred Term (PT) and System Organ Class (SOC). An AE that occurs more than once within each subject will be counted only once in the summaries, i.e., where a subject has the same adverse event, based on preferred terminology, reported multiple times, the subject will only be counted once at the preferred terminology level in adverse event summary tables. Where a subject has multiple adverse events within the same system organ class, the subject will be counted only once at the system organ class level in adverse event summary tables. When reporting adverse events by NCI-CTCAE grade, summary tables will be provided using the worst NCI-CTCAE grade.

The following AE summary tables will be provided:

- Overall Summary of Treatment-Emergent Adverse Events
- Summary of Treatment-Emergent Adverse Events by SOC and PT
- Summary of Treatment-Emergent Adverse Events Reported $\geq 10\%$ by Preferred Term
- Summary of Treatment-related Treatment-Emergent Adverse Events by SOC and PT
- Summary of Treatment-Emergent Serious Adverse Events by SOC and PT
- Summary of Treatment-Emergent Serious Adverse Events Reported $\geq 2\%$ by Preferred Term
- Summary of Treatment-related Treatment-Emergent Serious Adverse Events by SOC and PT
- Summary of Treatment-Emergent Adverse Events by Worst NCI-CTCAE Grade, SOC and PT
- Summary of Treatment-related Treatment-Emergent Adverse Events by Worst NCI-CTCAE Grade, SOC and PT
- Summary of NCI-CTCAE Grade 3 or Higher Treatment-Emergent Adverse Events by SOC and PT
- Summary of NCI-CTCAE Grade 3 or Higher Treatment-Emergent Adverse Events Reported $\geq 5\%$ by Preferred Term
- Summary of Treatment-related Treatment-Emergent Adverse Events with NCI-CTCAE Grade 3 or Higher by SOC and PT

- Summary of Treatment-Emergent Adverse Events Leading to Dose Reduction by SOC and PT

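### Non-serious, clinically graded AEs carried over from the parent study need no record or grade before the first rollover dose, so the SAP's worsening rule lacks its input

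*Protocol*

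**What the plan says.** **Collection before first dose.** Protocol 10.2.2.1 limits reporting between consent and first rollover dose to "all SAEs and any AEs that are related to protocol-required procedures".

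**Collection after first dose.** Protocol 10.2.2.2: "Following initiation of study drug, collect all AEs, regardless of cause or relationship, until 30 days after last administration of study drug". It gives no rule for an AE already under way at that moment. Protocol 10.2.2.5 has sites elicit events with a question such as "have you experienced any new or changed symptoms since we last asked/since your last visit".

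**Entry data.** In the Schedule of Assessments (Protocol Table 1) the only history item at Screening is "Prior sacituzumab govitecan parent study"; there is no row for medical history or ongoing AEs. SAP 5.2 lists parent-study identifiers, last cycle, last dose and its date, and adds that, where available, the "number of dose reduction and each dose reduction date and reason in parent study will also be listed". SAP 5.4 covers demographics only. None of these carries an AE term or grade.

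**Analysis.** SAP 6.2 defines treatment-emergent AEs as "any AEs that begin or worsen on or after the start of study drug through 30 days after the last dose of study drug" and restricts the AE summaries to them. Protocol 11.3.3 defines them as "any AE that begins on or after the date of first dose of study drug", with the same 30-day end but no provision for worsening.

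**The concern.** The SAP's rule has two limbs. The first needs an onset date. The second needs a grade before first dose to compare with the grade afterwards, and for clinically graded, non-serious events the plan requires none.

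In a trial that starts subjects on a new drug this would be a small gap. Here all subjects are on the drug when they enter (inclusion criterion 2), and earlier toxicity excludes them only if it led to permanent discontinuation (exclusion criterion 3). The plan therefore admits subjects with low-grade diarrhea, neuropathy or fatigue. Diarrhea and neuropathy are AEs of special interest in SAP Table 1, and fatigue is among the most common AEs in Protocol 1.3.4.

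The study's sole objective is long-term safety. Toxicity that persists from the parent study is central to that objective, and it is the kind of event for which the counting rule is least well supported.

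**Working it through.** The documents state no figure on this point, so the check sets the rules side by side and then illustrates with assumed rates.

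**Step 1. Which events have an entry record?**

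| Event present at entry | Pre-dose record required? | Source |
|---|---|---|
| Laboratory abnormality | Yes: the last value before first dose is baseline, with CTCAE shift tables | SAP 6.5; Protocol 11.3.3 |
| SAE after consent | Yes | Protocol 10.2.2.1, 10.2.2.3 |
| AE caused by a protocol-required procedure | Yes | Protocol 10.2.2.1 |
| Other non-serious, clinically graded AE | No term, onset date or grade required | Protocol 10.2.2.1, Table 1; SAP 5.2, 5.4 |

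Only the last row is a gap. For laboratory data the plan already uses the right device: Protocol 11.3.3 asks for a rise of at least one toxicity grade from baseline.

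**Step 2. How is a carried-over event counted?**

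| Course and recording | Protocol 11.3.3 | SAP 6.2 |
|---|---|---|
| Unchanged, not entered | Absent | Absent |
| Unchanged, entered with true onset | Not treatment-emergent | Not treatment-emergent; in the all-AE listing only |
| Unchanged, entered with a post-dose onset | Counted | Counted |
| Worsened, entered with true onset | Not treatment-emergent | Counted only if the entry grade is known |
| Worsened, entered as a new AE with a post-dose onset | Counted | Counted |

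The same clinical course can be summarized or not, depending on how it is entered. For a worsened event entered with its true onset, the two documents also differ from each other.

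**Step 3. Illustration of size.** Assumed rates; N = 200 is the planned maximum.

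*One preferred term.* Suppose the term arises newly in 5% of subjects and is ongoing at entry in a further 5% to 30%, with no overlap.
- Carried-over cases not counted: 200 × 0.05 = 10 subjects (5%).
- All carried-over cases counted as new: 200 × (0.05 + 0.05) = 20 to 200 × (0.05 + 0.30) = 70 subjects (10% to 35%).
- The SAP 6.2 table of AEs reported in at least 10% has its cut-off at 200 × 0.10 = 20 subjects, so the term could be in or out of that table.

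*Any AE.* Suppose a share *a* = 80% has a new AE and a share *c* = 10% to 50% has an ongoing one, independently. The percentage with any AE if carried-over events are counted is *a* + (1 − *a*) × *c*.
- *c* = 10%: 0.80 + 0.20 × 0.10 = 82%.
- *c* = 50%: 0.80 + 0.20 × 0.50 = 90%.
- Carried-over events not counted: 80%.

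These are outer limits, because they compare no carried-over case counted with every one counted. A subject with any new AE is already in the any-AE count, so that endpoint is less sensitive than the preferred-term tables.

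**The case against.** The strongest reply is Protocol 10.2.1.1. It makes worsening of a condition already present an AE in itself, and it says that expected ups and downs of such a condition, short of clinically significant worsening, are not AEs. Read with the elicitation question in 10.2.2.5, it tells sites to report a worsening and not to re-enter unchanged toxicity. This stands. A reader might infer that the plan loses later worsening, or that sites will report old toxicity as new. The documents support neither: the first runs against 10.2.1.1, and the second is a prediction about sites that would depart from it. What remains is that separating a worsening from a fluctuation requires knowing the starting grade.

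Other replies stand in part:

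- Some traces of entry toxicity exist. Protocol 6.4 records prior medications with their indication, and SAP 5.2 lists parent dose-reduction reasons where available. Neither gives a grade at entry.
- The previous subject number in SAP 5.2 makes linkage to parent AE data possible. Neither document plans it.
- The eCRF instructions are not among the documents, and the reach of the AE row in Table 1 is hard to read from the extracted text. Section 10.2.2.1 is explicit, though, and Table 1's AE footnote deals with events ongoing at end of treatment, not at entry.
- Under the Protocol's definition alone, no starting grade is needed. That is correct, but the SAP uses the other definition. The SAP is based on the original protocol dated 16 December 2019, so the two need aligning in any case.

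**Conclusion.** The point holds for non-serious, clinically graded AEs ongoing at the first rollover dose. For these the plan requires no entry record or grade, while SAP 6.2 relies on one. Worsening can still be reported, but it cannot be distinguished consistently from continuation. Persistent toxicity that is not shown to have worsened drops out of the summary tables and appears at most in a listing. Laboratory abnormalities and SAEs after consent are outside the point.

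The size cannot be derived from the documents. The 5% versus 10% to 35% for a preferred term, and the 80% versus 82% to 90% for any AE, rest wholly on assumed rates and describe extremes of recording practice. A reader might also multiply an assumed share with ongoing AEs by 200 and call the result misclassified subjects; at 30% to 60% that would be 60 to 120. The documents give no such share, and require subjects to be tolerating therapy at enrollment. Any such count would be of subjects exposed to the ambiguity, not of errors. Nor do the documents show that the any-AE endpoint would be materially inflated.

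The change is worth making because the study is about long-term safety, the fix is cheap, and entry status is hard to reconstruct later unless parent data are linked.

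**What to change.** 1. **Protocol 10.2.2.1 and Table 1:** record each AE ongoing at the first rollover dose, before dosing on Cycle 1 Day 1, with term, onset date and current CTCAE grade. Pre-fill it, or link it, from the parent AE data through the previous subject number.
2. **SAP 6.2:** count such an event as treatment-emergent only if its grade rises above the entry grade. Add a separate row to the AE summaries for events ongoing at entry and not worsened.
3. **Protocol 11.3.3 and SAP 6.2:** use one definition of treatment-emergent AE, covering both new onset and worsening.

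The cost is one eCRF page or a data transfer from the sponsor's parent studies, a short SAP addition and one table row, with a small burden at entry. It adds no study procedure and changes nothing in clinical management.
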